## **2) Brief Summary:**

Priming stimulation is a highly promising tool to boost the beneficial effects of therapeutic repetitive transcranial magnetic stimulation (rTMS) in psychiatry. The potentiating effects of priming stimulation, however, depend on the time interval between the priming and the test stimulation. Although it is known that too short and too long intervals have no effects, systematic studies that identify the time needed to maximize efficacy have not yet been done. Thus, there is a need for studies to investigate the effects of priming stimulation in order to fully utilize the potential benefits and advantages of this promising new rTMS protocol. Here we propose a research program that will systematically investigate the neuromodulatory process underlying priming stimulation to enhance metaplasticity in the left dorsolateral prefrontal cortex (DLPFC) – one of the main targets for therapeutic rTMS – in individuals with subclinical depression.

The brain is a highly plastic organ and its activity can be influenced using rTMS. At the same time, the brain also has a mechanism – called homeostatic metaplasticity – which counteracts extreme plastic changes. Homeostatic metaplasticity therefore can limit the beneficial effects of brain stimulation interventions. However, priming stimulation protocols that include both a priming and a test stimulation session may utilize homeostatic metaplasticity to increase the beneficial effects of brain stimulation, although the optimal treatment parameters for priming are not known. Moreover, little is known about homeostatic metaplasticity in the DLPFC, an area that is particularly relevant for psychiatric conditions given its role in the top-down control of emotions. Here, we will systematically study metaplasticity using priming theta-burst stimulation (TBS), a potent form of rTMS in the left DLPFC. The optimized stimulation intensity will be investigated by a pilot study. Changes in blood oxygenation that signal brain activity changes will be assessed using functional near-infrared spectroscopy (fNIRS) at rest and during engagement in several cognitive tasks. The findings from this study will (1) elucidate the optimal time interval between priming and test stimulation; (2) elucidate the influence of priming TBS on emotion discrimination as well as executive function and its underlying brain activity in subclinical depression; and (3) validate homeostatic metaplasticity in the left DLPFC.

Subclinical depression has serious consequences for the quality of life and is associated with considerable economic costs but adequate treatments are poorly explored. Therefore, by systematically testing priming stimulation and investigating its underlying neural processes, this study will pave the way towards developing adequate antidepressant treatments that will reduce personal suffering, reduce costs and occupational disability.

**3) Detailed Description:** Please refer to the ECS proposal

**4) Primary Disease or Condition being studied in the trial, or the focus of the study:**  
Subclinical Depression

**5) Keywords:** Priming Stimulation, Theta-Burst Stimulation, Functional NIRS, Emotion Discrimination, Subclinical depression

**6) Primary Purpose:** Optimization of stimulation parameters for a priming stimulation protocol

**7) Study Phase:** N/A

**8) Intervention Study Model:** Parallel, sham-control

**9) Model Description:** (Objectives)

The proposed research has two primary objectives.

The first objective is to understand the effects of priming stimulation timing of the left DLPFC using fNIRS at rest. The time window between priming cTBS and test iTBS will be either 0, 10, or 20 minutes. We hypothesize that 0 minutes will eliminate the effect of the test iTBS, whereas 10 minutes will potentiate it; 20 minutes will have no effect (i.e., result in no difference, relative to sham priming).

The second objective is to evaluate the effects of priming stimulation in the context of facial emotion processing and executive function in subclinical depression. Previous evidence indicates that DLPFC stimulation modulates affective processing on the neural and behavioral level. We hypothesize that optimal priming stimulation will affect reaction times in an emotion-specific way and will reduce the negative bias observed in subclinical depression.

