### **Outcome 3: Secondary Outcome Measure**

Title: Behavioral measures including reaction times and recognition accuracy

Description: Reaction times and accuracy during the cognitive tasks will be evaluated before and after stimulation

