## **13) Statistical Analysis Plan:**

fNIRS data analysis will follow the standard processing steps. This includes spatial registration (recording of standard cranial landmarks nasion, inion, left and right ear, and the 3D locations of the fNIRS probes); transformation to MNI space [39]; band-pass

filtering for motion artifact removal; and estimation of the hemodynamic response function using GLM, as implemented in the NIRS Toolbox for MATLAB. Comparisons between baseline and task HbO will reveal task-related de/activations, corrected for multiple comparisons (52 channels). Average HbO changes will then be determined for each channel and each measurement and entered into second-level analysis. Similarly, means of HbO for pre and post-stimulation will be entered into second-level analysis.

A t-test between pre- and post-stimulation in condition 1 will be performed to test hypothesis 1. Hypothesis 1 will be supported if there is a significant increase in prefrontal HbO after stimulation.

A t-test between condition 2 and 1 using change scores will be performed to test hypothesis 2. Hypothesis 2 will be supported if there is a significant stronger change in HbO in condition 1 compared to condition 2

A t-test between condition 3 and 1 using change scores will be performed to test hypothesis 3. Hypothesis 3 will be supported if there is a significant stronger change in HbO in condition 3 compared to condition 1.

A t-test between pre- and post-stimulation in condition 4 and between change scores of condition 1 and 4 will be performed to test hypothesis 4. Hypothesis 4 will be supported if there is a significant increase in prefrontal HbO after stimulation, but no significant difference in change scores between condition 1 and 4.

Regarding the three exploratory hypotheses about participants' behavior (reaction times, hits and misses) and HbO changes during cognitive tasks, linear mixed models will be conducted to determine differences between conditions, followed by post-hoc pairwise comparisons. Here, a three-way interaction between time, condition and emotion will be evaluated and followed by post-hoc two-way interactions and pairwise comparisons.

Hypothesis E1 will be supported if there is a significant change in HbO and/or behavioral measures in condition 1 in some (e.g. sad) but not other emotions (e.g. happy) after stimulation (following a post-hoc 2-way interaction between time and emotion).

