Hypothesis E2 will be supported if there is a significant interaction between time, emotion and conditions 2 and 1.

Hypothesis E3 will be supported if there is a significant interaction between time, emotion and conditions 3 and 1.

Hypothesis E4 will be supported if there is a significant change in condition 4 in some (e.g. sad) but not other emotions (e.g. happy) after stimulation (following a post-hoc 2-way interaction between time and emotion).

Finally, two t-tests comparing ERA- recognition accuracies between subclinically depressed and control participants and between pre and post stimulation in the sample of subclinically depressed participants will be performed in order to test hypotheses E5 and E6, respectively.

Hypothesis E5 will be supported if recognition accuracy is reduced in participants with subclinical depression compared to the control sample.

Hypothesis E6 will be supported if recognition accuracy will be increased after stimulation compared to baseline in participants with subclinical depression.

Behavioral data will be analyzed using the IBM SPSS software (<http://www-01.ibm.com/software/analytics/spss/>). The alpha level will be set at 0.05, adjusted for multiple comparisons using the Bonferroni-Holm procedure. For GLM, post-hoc pairwise comparisons will be corrected using Fisher least significant difference procedure in accordance with the closed test principle, i.e., post hoc comparisons will be declared nonsignificant if the global p value of the main- or interaction effect is nonsignificant, but carried out without further correction in case of a significant global effect.

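### Objective 2 predicts a reduced negative bias, but no listed outcome or decision rule (E1 to E6) is specified to test that reduction

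*Combined protocol and SAP*

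**What the plan says.** Section 9 (Model Description) presents two primary objectives. For the second, it predicts that optimal priming "will affect reaction times in an emotion-specific way and will reduce the negative bias observed in subclinical depression".

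The behavioural outcome in section 11 (Outcome 3) is titled "Behavioral measures including reaction times and recognition accuracy", and its description reads "Reaction times and accuracy during the cognitive tasks will be evaluated before and after stimulation".

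Section 13 (Statistical Analysis Plan) refers to exploratory hypotheses about "participants' behavior (reaction times, hits and misses) and HbO changes during cognitive tasks". These are analysed by linear mixed models in which "a three-way interaction between time, condition and emotion will be evaluated and followed by post-hoc two-way interactions and pairwise comparisons".

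The decision rules are:
- **E1 and E4:** a significant change in condition 1 (E1) or condition 4 (E4) "in some (e.g. sad) but not other emotions (e.g. happy) after stimulation".
- **E2 and E3:** a significant interaction of time, emotion and condition (2 v 1 and 3 v 1 respectively).
- **E5:** lower recognition accuracy in subclinically depressed participants than in controls.
- **E6:** "Hypothesis E6 will be supported if recognition accuracy will be increased after stimulation compared to baseline in participants with subclinical depression".

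Sections 9, 11 and 13 name no false-alarm rate, response criterion, rate of labelling non-negative faces as negative, or other bias index. None of E1 to E6 is worded as a reduction in negative bias.

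**The concern.** If negative bias is read as a tendency to give negative labels, removing it lowers hits on sad faces and raises hits on the other faces. Accuracy pooled over emotions adds a loss to a gain, so most of the effect cancels. Accuracy also mixes bias with sensitivity, because a participant can become more accurate with no change in bias.

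The rules that do look at emotions separately ask only whether something differs by emotion. They do not ask whether responses moved away from negative.

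Two wrong reports are therefore possible under the plan as written. A real reduction in bias could be reported as no effect (E6). An increase in bias could be accepted as support (E1 to E4). A third risk is that a bias score is chosen after the data have been seen, because none is fixed beforehand. All this bears on a prediction that belongs to a stated primary objective.

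**Working it through.** **No figure to reproduce.** The documents give no hit rate, bias, SD or power for these measures. Every value of d', b and SD below is an assumption, used to show how the measures behave. The only input from the documents is the sample of 80 (section 10, Interventions).

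**Step 1: model.** Equal-variance signal detection, two choices (sad or happy), equal numbers of each face. Let d' be sensitivity and b the bias toward sad in SD units (b = −c, where c is the criterion).
- Sad hits = Φ(d'/2 + b)
- Happy hits = Φ(d'/2 − b)
- Pooled accuracy = mean of the two
- With no bias, all three equal Φ(d'/2)

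**Step 2: pooled accuracy, as E5 and E6 read.**

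| d' | No bias | b = 0.3 | Gain on removal (points) | b = 0.5 | Gain on removal (points) |
|---|---|---|---|---|---|
| 1.0 | 69.15% | 68.37% | 0.8 | 67.07% | 2.1 |
| 1.5 | 77.34% | 76.34% | 1.0 | 74.65% | 2.7 |
| 2.0 | 84.13% | 83.06% | 1.1 | 81.23% | 2.9 |
| 3.0 | 93.32% | 92.45% | 0.9 | 90.93% | 2.4 |

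One row in full, for d' = 1.5 and b = 0.3: sad hits Φ(1.05) = 85.31%, happy hits Φ(0.45) = 67.36%, mean 76.34%. Without bias, Φ(0.75) = 77.34%. Gain 1.0 point.

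For a large bias (b = 0.8) the gain is 4.9 to 7.0 points over the same range of d', so the insensitivity is confined to small and moderate bias. In a simulated six-choice task (d' 1.5 or 2.5), removing a bias of 0.3 or 0.5 raises pooled accuracy by about 0.3 to 1.1 points, and removing 0.8 by about 3 points.

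**Step 3: what such a gain means for E6.** Paired comparison, all 80 participants, two-sided 0.05 without multiplicity adjustment. Power = Φ(δ/(SD/√80) − 1.96).

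| Change δ (points) | SD of change 0.08 | 0.10 | 0.15 |
|---|---|---|---|
| 0.9 | 17% | 12% | 8% |
| 1.3 | 31% | 21% | 12% |
| 3.0 | 92% | 77% | 43% |

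For example, with δ = 0.013 and SD 0.08: 0.013/(0.08/8.944) = 1.453, and Φ(1.453 − 1.96) = 31%.

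**Step 4: hits by emotion, as the mixed model reads.** Removing b = 0.3 changes sad hits by −9.7 points and happy hits by +11.2 at d' = 1.0, and by −3.1 and +4.8 at d' = 3.0. These measures do respond to bias.

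**Step 5: can bias be told from sensitivity?** From one emotion alone, no. A sad hit rate of 84.1% arises from (d' 1.0, b 0.5), (1.5, 0.25) or (2.0, 0). From both emotions in a two-choice task, yes, because a missed happy face is a sad false alarm. With sad hits 84.13% and happy hits 50.00%, d' = z(0.8413) + z(0.5000) = 1.0 and b = [z(0.8413) − z(0.5000)]/2 = 0.5. With more than two options, the distribution of wrong answers is needed.

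**Step 6: direction.** Under E1 and E4, a rise in sad hits with no change in happy hits and a fall in sad hits with no change in happy hits count equally. E2 and E3 need only a significant interaction. No rule separates a reduction in bias from an increase.

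**The case against.** Four objections have weight.

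1. **Hits by emotion are analysed.** A reader might infer that the listed measures cannot separate bias from sensitivity and hardly move when bias changes. The documents do not support that as a general statement. It is true of pooled accuracy with small or moderate bias, and of one emotion's hits taken alone. The planned time by condition by emotion model uses hits by emotion, which shift by several points, and in a two-choice task hits on both emotions recover both quantities. What remains is that the plan neither combines them into a bias measure nor states the pattern that would count as a reduction.

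2. **Bias may mean reaction times.** The documents do not define negative bias. Objective 2 names emotion-specific reaction times in the same sentence, and section 11 lists an emotional Stroop task. A reaction-time bias is compatible with the text, so it cannot be said that no listed behavioural measure could bear on the claim. But no reaction-time bias score or direction is given either.

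3. **E5 and E6 do not claim to test bias.** They are worded as accuracy hypotheses. This is correct, and it leaves the bias prediction without a test. Nor do the rules for E1 to E4 score a fall in sad hits as impairment; it could count as support. The fault there is the missing direction.

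4. **The task details lie elsewhere.** Section 3 refers to a separate proposal for the detailed description. The number of response options, the use of neutral faces and the recording of each chosen label are not given here, so it cannot be taken as fact that a full response matrix exists.

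**Conclusion.** The point holds as a mismatch between an objective and its tests. A predicted reduction in negative bias, part of a stated primary objective, has no prespecified score and no rule with a direction.

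Pooled accuracy in E5 and E6 is a weak proxy: about 1 to 3 points for a bias of 0.3 to 0.5 SD in a two-choice model, but about 5 to 7 points for 0.8 SD. At n = 80, power for a change near 1 point is roughly 8% to 31%. For 3 points it is 43% to 92%, so the upper end of that range could be detected if the SD of change is small. These figures rest on an equal-variance model and on assumed d', bias and SD of change.

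The conclusion that no decision rule tests a reduction follows from the wording of E1 to E6 and does not depend on those assumptions. The change is worth making but not critical, since the SAP labels these hypotheses exploratory and resting HbO, the primary outcome, is unaffected.

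**What to change.** - **Define the score.** Prespecify a negative-bias score for the emotion discrimination task: either the signal-detection criterion or the proportion of non-negative faces labelled negative. In a two-choice task this can be computed from hits on both emotions. With more options, first confirm that the task records the response chosen.
- **Attach it to a test with a direction.** In the condition 3 v 1 comparison (E3), state that support requires a greater reduction in the bias score in condition 3.
- **Use it in E5.** Report the bias score beside accuracy in the comparison of depressed and control participants.
- **Keep sensitivity and accuracy apart.** Report a sensitivity measure such as d' separately, and keep recognition accuracy as its own outcome.
- **If a reaction-time bias is intended,** define that score and its direction instead.

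The cost is SAP wording and rescoring, with no new testing if responses are already recorded by label. The downside is one more derived variable in an exploratory family.

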**10) Interventions:**

Number of Arms: 4

Allocation: Randomized

Enrollment Type: Anticipated

Number of Subjects: 80 participants with subclinical depression

Arm 1: Control

Arm Title: Priming sham TBS – followed by iTBS after an ISI of 0 minutes

Arm Description: self-explanatory, see Arm Title

Arm 2: Experimental

Arm Title: Priming cTBS – followed by iTBS after an ISI of 0 minutes

Arm Description: self-explanatory, see Arm Title

Arm 3: Experimental

Arm Title: Priming cTBS – followed by iTBS after an ISI of 10 minutes

Arm Description: self-explanatory, see Arm Title

Arm 4: Experimental

Arm Title: Priming cTBS – followed by iTBS after an ISI of 20 minutes

Arm Description: self-explanatory, see Arm Title

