## **11) Outcome Measures:**

### **Outcome 1: Primary Outcome Measure**

Title: HbO during rest before and after stimulation (raw values and change scores)

Description: Prefrontal neural activity will be measured using fNIRS before (baseline) and about 10-15 minutes after the stimulation (delay will be recorded). TBS-induced blood oxygen changes (HbO) at rest will be evaluated in the frontal cortex

Time Frame: baseline, post intervention

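### Sham priming is given only at a 0-minute interval, so H3 and the between-arm part of H4 mix priming with about 10 or 20 extra minutes since baseline

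*Combined protocol and SAP*

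**What the plan says.** Section 10 (Interventions) gives "Number of Arms: 4" and "Number of Subjects: 80 participants with subclinical depression". The control is "Arm Title: Priming sham TBS – followed by iTBS after an ISI of 0 minutes". Arm 2 is "Arm Title: Priming cTBS – followed by iTBS after an ISI of 0 minutes", Arm 3 is "Arm Title: Priming cTBS – followed by iTBS after an ISI of 10 minutes", and Arm 4 is the same with 20 minutes. No sham arm has a 10- or 20-minute interval, and no equalising wait is described for Arms 1 and 2.

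Section 11, Outcome 1, measures resting HbO "before (baseline) and about 10-15 minutes after the stimulation (delay will be recorded").

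Section 9 (Model Description) makes the timing of priming the first objective. It predicts abolition of the iTBS effect at 0 minutes, potentiation at 10, and that "20 minutes will have no effect (i.e., result in no difference, relative to sham priming").

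Section 13 (Statistical Analysis Plan) tests H2 as condition 2 against 1. For H3 it states: "A t-test between condition 3 and 1 using change scores will be performed to test hypothesis 3". H4 needs a significant pre-post increase in condition 4 and a non-significant difference in change scores between conditions 4 and 1. No adjustment for elapsed time is specified. Alpha is 0.05 with Bonferroni-Holm; the family of tests and the sidedness are not stated.

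**The concern.** A control comparison isolates priming only if the arms differ in nothing else that could move the outcome. Here, conditions 3 and 4 differ from condition 1 in whether priming was active and also in how long the participant waited between baseline and the post scan. If resting HbO, or the response to iTBS, changes over 10 to 20 minutes of waiting, that change goes into the H3 and H4 contrasts and is read as an effect of priming.

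The stake is the first primary objective. H3 is the only test of the predicted 10-minute benefit, and the between-arm part of H4 is the only test of the predicted 20-minute null against sham. H4 is exposed in both directions: drift can make condition 4 differ from control when priming does nothing, or cancel a real difference and so produce the predicted null.

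**Working it through.** **1. What each contrast changes.** Let S be the stimulation time common to all arms. As written, and if nothing else equalises the sessions, baseline-to-post time is S + ISI + 10-15 minutes:

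| Arm | Priming | ISI (min) | Baseline to post (min) | Extra v Arm 1 (min) |
|---|---|---|---|---|
| 1 | sham | 0 | S + 10-15 | – |
| 2 | cTBS | 0 | S + 10-15 | 0 |
| 3 | cTBS | 10 | S + 20-25 | 10 |
| 4 | cTBS | 20 | S + 30-35 | 20 |

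H2 therefore changes priming only, H3 changes priming and adds 10 minutes, and the between-arm part of H4 changes priming and adds 20 minutes. The delay from iTBS to the post scan is nominally the same in all arms; the mismatch lies before iTBS.

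**2. Can analysis separate the two?** Not with this design. No sham participant has a 10- or 20-minute interval, so there is no sham reference at those times. The delay to be recorded runs from stimulation to scan, not over the ISI. Comparing Arms 2, 3 and 4 does not help, because ISI and elapsed time move together there.

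**3. Possible size (illustration).** The plan gives no SD, effect size, power or allocation ratio, so its sample size of 80 cannot be reproduced. Assumptions: equal allocation, 80 / 4 = 20 per arm; two-sided tests; no true priming effect; linear upward drift of 0.25 or 0.5 SD of the change score per extra 10 minutes. The drift is assumed; the 10- and 20-minute differences come from the arm definitions.

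For a two-sample t-test with n = 20 per arm, df = 38 and noncentrality d × √(n/2) = d × 3.162. The critical value is 2.024 at 0.05 and 2.622 at 0.05 / 4 = 0.0125, the strictest Holm step if the family is taken as H1-H4.

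| Contrast | Bias d (SD) | Noncentrality | P(significant, upward), 0.05 | Same, 0.0125 |
|---|---|---|---|---|
| no drift | 0 | 0 | 0.025 | 0.006 |
| H3 (3 v 1) | 0.25 | 0.79 | 0.117 | 0.041 |
| H3 (3 v 1) | 0.50 | 1.58 | 0.338 | 0.163 |
| 4 v 1 | 0.50 | 1.58 | 0.338 | 0.163 |
| 4 v 1 | 1.00 | 3.16 | 0.869 | 0.703 |

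The 4 v 1 rows are not false support for H4. H4 needs a non-significant difference, so these are trials in which it fails wrongly.

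**4. Drift in the opposite direction (0.05, unadjusted).** A true H3 effect of 0.8 SD has power 0.69. Downward drift of 0.25 / 0.5 SD leaves a net 0.55 / 0.30 SD and power of about 0.40 / 0.15. For 4 v 1, a true difference of 0.8 SD is non-significant with probability 0.31 without drift. Downward drift of 0.25 SD per 10 minutes (0.5 SD over 20) leaves 0.30 SD, and that probability becomes 0.85.

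**5. Full predicted pattern.** Simulating three arms of 20 with a shared Arm 1, no priming effect and the drifts in step 3, H3 is significant upward and 4 v 1 is non-significant in about 4% / 1% of trials at 0.05.

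**The case against.** - **Drift is assumed.** The documents give neither its size nor its direction, nor any evidence that it exists. This stands, so the percentages above illustrate the risk and do not estimate it. The structural mismatch does not depend on them.
- **Arm 4 is a partial check.** The predicted result is not monotone: potentiation at 10 minutes, none at 20. Linear drift biases Arm 4 twice as much as Arm 3 and so works against that pattern, as step 5 shows. This stands, but it does not protect H3 when read alone, which is how the plan decides it, and it does not exclude drift of other shapes.
- **The plan applies Holm.** At 0.0125 the H3 figures fall to about 4% / 16%. This stands if the family is H1-H4, which the plan does not say. They still exceed the 0.6% expected in that direction at that level.
- **The fuller description lies elsewhere.** Section 3 defers detail to the ECS proposal, which was not supplied and might equalise session length. If so, the mismatch disappears, but the plan should say so.

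Two stronger readings are tempting and unsupported. A reader might infer that Arms 3 and 4 cannot be masked, since any wait between stimulations implies active priming. That holds only for someone who knows the arm list; the design is parallel, and the documents neither claim masking nor say what participants are told. A reader might also infer that H3 and H4 are certainly biased. The documents support only that a priming interpretation needs an assumption they do not state.

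**Conclusion.** The concern holds as a confound in the design. H2 isolates priming. H3 and the between-arm part of H4 compare active priming plus about 10 or 20 extra minutes with sham priming and no extra wait. Attributing either result to priming requires that the waiting changes neither resting HbO nor the response to iTBS, and the plan neither states nor tests this. The consequence could be negligible or substantial: under the assumed drifts, false support for H3 alone runs from about 4% to 34% depending on the drift and the Holm step, while the complete predicted pattern arises by drift in only about 1% to 4% of trials at unadjusted 0.05. This should be fixed before recruitment, because the planned analysis cannot recover the separation afterwards. It does not invalidate H2 or the trial as a whole.

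**What to change.** Equalise baseline-to-post time without changing any priming-to-iTBS interval. Add a quiet wait between baseline fNIRS and priming of 20 minutes in Arms 1 and 2, 10 minutes in Arm 3 and 0 minutes in Arm 4. Wait plus ISI is then 20 + 0, 20 + 0, 10 + 10 and 0 + 20, which is 20 minutes in every arm, and baseline-to-post time is S + 30-35 minutes throughout. If the ECS proposal already equalises session length, state that in this document instead.

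The cost is a protocol amendment, longer sessions in Arms 1 to 3 and, at 20 per arm, 20 × 40 + 10 × 20 = 1,000 minutes (about 17 hours) of lab time. No extra participants are needed. The wait matches time since baseline but not the gap between the two stimulations, so any effect of that gap itself should be acknowledged as a limitation.

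If the wait is not added, state in section 13 that H3 and the between-arm part of H4 compare priming plus waiting with no waiting, and word the conclusions accordingly.
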